## 1. RCT Details

This section provides a high-level overview of a **published** RCT that the described real-world evidence study is trying to replicate as closely as possible given the remaining limitations inherent in the healthcare databases.

### 1.1 Title

**Oral Apixaban for the Treatment of Acute Venous Thromboembolism ([AMPLIFY](#))**

### 1.2 Intended aim(s)

To compare the risk of symptomatic, recurrent venous thromboembolism (VTE) in patients with symptomatic deep vein thrombosis (DVT), pulmonary embolism (PE), or both for apixaban versus standard therapy of warfarin.

### 1.3 Primary endpoint for replication

The primary outcome of the study was symptomatic, recurrent VTE or death related to VTE

### 1.4 Required power for primary endpoint and noninferiority margin (if applicable)

Assuming a non-inferiority margin of 1.80, it was determined that 4,094 patients would be needed to achieve 90% power to conclude noninferiority of apixaban over standard therapy at one-sided alpha level of 0.025.

### 1.5 Secondary endpoint for replication (assay sensitivity) and RCT finding

Major bleeding; RR= 0.31 (95% CI 0.17–0.55)

### 1.6 Trial estimate

RR = 0.84 (95% CI 0.60-1.18) comparing apixaban vs standard therapy (Agnelli et al., 2013)

## 2. Person responsible for implementation of replication in Aetion

[name] implemented the study design in the Aetion Evidence Platform. She is not responsible for the validity of the design and analytic choices. All implementation steps are recorded and the implementation history is archived in the platform.

## 3. Data Source(s)

[figure not shown]
Optum, MarketScan, Medicare

#### 4. Study Design Diagram

The study design diagram visualizes key aspects of the longitudinal study design for expedited review.

Figure 1.

#### Design Diagram – AMPLIFY TRIAL REPLICATION

## 5. Cohort Identification

### 5.1 Cohort Summary

This study will involve a new user, parallel group, propensity score-matched, retrospective cohort study design comparing apixaban to warfarin users. The patients will be required to have continuous enrollment during a baseline period of 180 days before initiation of apixaban or warfarin (index date). We will restrict the analyses to patients with a diagnosis of proximal DVT, PE, or both.

### 5.2 Important steps for cohort formation

New use of apixaban, exposure, and warfarin, comparator, is defined as no use of either therapy in the 180 days prior to index date.

#### 5.2.1 Eligible cohort entry dates

Market availability of apixaban in the U.S. for treatment of deep vein thrombosis and pulmonary embolism started on August 21, 2014

- For Medicare: August 21, 2014 – December 31, 2017 (end of available data)
- For Marketscan: August 21, 2014 – December 31, 2018 (end of available data)
- For Optum: August 21, 2014 – March 31, 2020 (end of available data)

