### 6.2 Covariates:

- Age
- Sex
- Combined Comorbidity Index (CCI), measured over the baseline covariate assessment period, defined as 180 days prior to and including index date

Covariates listed above represent only a small subset of covariates that will ultimately be controlled for in the design and analysis. We use the covariates above only for initial feasibility analyses to judge whether there is likely to be sufficient overlap between treatment groups to proceed with the study. Remaining covariates are defined only after the study has passed the initial feasibility analysis and the initial power assessment and are listed in Table 1 (**Appendix B**).

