## 9. Balance Assessment

**Action report links:**

Optum: <https://bwh-dope.aetion.com/projects/details/1484/results/64541/result/0>

Marketscan: <https://bwh-dope.aetion.com/projects/details/1481/results/64542/result/0>

Medicare: <https://bwh-dope.aetion.com/projects/details/1483/results/64543/result/0>

Date conducted: 1/19/2021

After review of initial feasibility and power analyses, complete creation of the remaining covariates from Section 6.2. Again, using the dummy outcome of a 90-day gap in database enrollment, complete a 1:1 PS-matched analysis. The PS should include the complete list of covariates.

- Provide plot of PS distributions stratified by treatment group.

Note- Please refer to **Appendix B**.

- Report covariate balance after matching.

Note- For Table 1, please refer to **Appendix B**.

- Report reasons for censoring by treatment group.

|  | Overall | Referent | Exposure |
|--|---------|----------|----------|
|--|---------|----------|----------|

|                                                                                                                               |                |                |                |
|-------------------------------------------------------------------------------------------------------------------------------|----------------|----------------|----------------|
| Dummy outcome                                                                                                                 | 67 (0.94%)     | 25 (0.70%)     | 42 (1.18%)     |
| Death                                                                                                                         | 103 (1.44%)    | 49 (1.37%)     | 54 (1.51%)     |
| Start of an additional exposure                                                                                               | 232 (3.25%)    | 175 (4.90%)    | 57 (1.60%)     |
| End of index exposure                                                                                                         | 4,701 (65.84%) | 2,202 (61.68%) | 2,499 (70.00%) |
| Specified date reached                                                                                                        | 857 (12.00%)   | 424 (11.88%)   | 433 (12.13%)   |
| End of patient enrollment                                                                                                     | 425 (5.95%)    | 198 (5.55%)    | 227 (6.36%)    |

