| Trial details- Secondary approval, Successful NI with label change                                                                                                                                                                                                                                                                                                                                                                                                                                   |                                                                                                                                                                                                                                                             |                                                                                                                                                                                                                                                                                  | ICD-10 codes are not listed in this document because of excel cell size limitations and excessive number of ICD-10 codes. Full ICD-10 code lists will be available in the above Google Drive Folder ( link above ). ICD-9 to ICD-10 code conversions were completed using a SAS macro that implements forward/backward mapping based on the CMS ICD-9 to ICD-10 mapping: https://www.ncbi.nlm.nih.gov/pmc/articles/PMC5300333/ |

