| Use of Low Intensity Statins; n (%)                                               | 169 (11.5%)         | 283 (10.2%)         | 0.04        | 245 (9.9%)          | 375 (9.7%)          | 0.01          | 788 (15.8%)     | 546 (16.0%)     | -0.01        | 1202 (13.5%)      | 1204 (12.0%)      | 0.04    |         |      |
| Use of High Intensity Statins; n (%)                                              | 127 (8.6%)          | 281 (10.1%)         | -0.05       | 216 (8.8%)          | 380 (9.8%)          | -0.03         | 562 (11.3%)     | 417 (12.2%)     | -0.03        | 905 (10.1%)       | 1078 (10.7%)      | -0.02   |         |      |
| Malignant hypertension; n (%)                                                     | ** (0.6%)           | ** (0.1%)           | 0.08        | 317 (12.9%)         | 101 (2.6%)          | 0.39          | 517 (10.4%)     | 93 (2.7%)       | 0.32         | #VALUE!           | #VALUE!           | #VALUE! |         |      |
| Cardiovascular stress test; n (%)                                                 | ** (0.7%)           | 12 (0.4%)           | 0.04        | 12 (0.5%)           | 26 (0.7%)           | -0.03         | 73 (1.5%)       | 60 (1.8%)       | -0.02        | #VALUE!           | 98 (1.0%)         | #VALUE! |         |      |
| Echocardiogram; n (%)                                                             | 909 (61.8%)         | 1,927 (69.2%)       | -0.16       | 1,573 (63.8%)       | 2,714 (70.1%)       | -0.13         | 2,941 (59.0%)   | 2,092 (61.4%)   | -0.05        | 5423 (60.8%)      | 6733 (66.9%)      | -0.13   |         |      |
| Number of BNP tests                                                               |                     |                     |             |                     |                     |               |                 |                 |              |                   |                   |         |         |      |
| ...mean (sd)                                                                      | 0.14 (0.44)         | 0.19 (0.52)         | -0.10       | 0.13 (0.44)         | 0.17 (0.48)         | -0.09         | 0.20 (0.56)     | 0.23 (0.56)     | -0.05        | 0.17 (0.51)       | 0.20 (0.52)       | -0.06   |         |      |

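### Calendar time of cohort entry is not directly controlled: the propensity score list has no index year or quarter, although entry opens on apixaban's first day for VTE and uses two coding systems

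*Combined protocol and SAP*

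**What the plan says.** Section 5.2.1 ties the start of entry to the drug's launch for the indication ("Market availability of apixaban in the U.S. for treatment of deep vein thrombosis and pulmonary embolism started on August 21, 2014") and gives three closing dates: "For Medicare: August 21, 2014 – December 31, 2017 (end of available data"), "For Marketscan: August 21, 2014 – December 31, 2018 (end of available data") and "For Optum: August 21, 2014 – March 31, 2020 (end of available data"). The windows are thus about 3.4, 4.4 and 5.6 years.

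Section 6.2 names age, sex and the comorbidity index for feasibility work. It says the remaining covariates are defined after the "initial power assessment and are listed in Table 1" (Appendix B). Section 9 then states: "The PS should include the complete list of covariates". Sections 13.1 and 13.2, for the primary and sensitivity analyses, hold headings only.

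Appendix A uses both coding systems for eligibility and for the VTE outcome: "ICD-9 to ICD-10 code conversions were completed using a SAS macro".

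**The concern.** When one treatment becomes available for an indication on the first day of the window and the comparator is already standard therapy, date of entry can predict treatment. If the recorded outcome rate also moves with date, through coding, admission practice or background care, then date is a confounder. A change of coding system inside the window adds a second route, because the same patient may be classified differently before and after it.

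The study aims to reproduce a trial hazard ratio of 0.84, so even a modest shift would blur the comparison. Index date is held for every patient, yet the plan neither balances it nor reports it. The nearest row in Table 1 counts days of prior database history, which is length of record rather than date.

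**Working it through.** **1. Is calendar time in the score?** I read both Table 1 panels in Appendix B, unmatched and matched. No row gives year, quarter or date of entry. No section describes matching or stratifying on entry date. The design diagram and propensity score plots were not readable in the copy reviewed.

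**2. Do the tables hint that era differs by arm before matching?** Three rows may be sensitive to coding era (warfarin vs apixaban, Appendix B):

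| Row | Database | Unmatched | Matched |
|---|---|---|---|
| CHA2DS2-VASc, mean | Optum | 1.73 vs 1.29 | 1.49 vs 1.52 |
| | MarketScan | 1.73 vs 1.08 | 1.24 vs 1.25 |
| | Medicare | 2.01 vs 1.45 | 1.55 vs 1.56 |
| Sleep disorder | Optum | 5.0% vs 2.9% | 4.3% vs 5.1% |
| | MarketScan | 8.0% vs 2.8% | 4.6% vs 4.8% |
| | Medicare | 7.5% vs 3.1% | 4.9% vs 4.7% |
| Malignant hypertension | Optum | 0.6% vs 0.1% | 0.2% vs 0.2% |
| | MarketScan | 12.9% vs 2.6% | 5.5% vs 6.2% |
| | Medicare | 10.4% vs 2.7% | 4.8% vs 4.3% |

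The MarketScan CHA2DS2-VASc standardised difference is 0.65 / √((1.43² + 1.06²)/2) = 0.52.

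**3. Do the score's likely components explain that gap?** MarketScan rows, warfarin vs apixaban: heart failure 8.0% vs 8.4%, hypertension 39.5% vs 41.3%, diabetes 15.5% vs 14.8%, any stroke 1.0% vs 0.9%, peripheral vascular disease 2.6% vs 1.7%, age 65–74 3.5% vs 3.0%, oldest age group 2.9% vs 2.4%, female 46.3% vs 49.1%.

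The documents do not define the score, so I assume these components, with weight 2 for stroke and the oldest age group and 1 for the rest:

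- Warfarin: 0.080 + 0.395 + 0.155 + 2(0.010) + 0.026 + 0.035 + 2(0.029) + 0.463 = 1.23
- Apixaban: 0.084 + 0.413 + 0.148 + 2(0.009) + 0.017 + 0.030 + 2(0.024) + 0.491 = 1.25

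The result does not hinge on the weights. The rows higher on warfarin exceed apixaban by 0.7 + 0.1 + 0.9 + 0.5 + 0.5 = 2.7 percentage points in total. With weight 2 on each of them and nothing counted against, they explain at most 0.054 of the 0.65 gap. The same sum in Optum and Medicare gives component gaps of 0.03 and 0.05 against observed gaps of 0.44 and 0.56.

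Two contrasts point the same way in MarketScan. HAS-BLED, whose row is labelled as covering both coding systems, is 1.88 vs 1.88. Obstructive sleep apnea is 15.2% vs 13.9%, while sleep disorder is 8.0% vs 2.8%.

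**4. What would the fix cost in power?** Section 10's figure reproduces. Expected events are d = 7,140 × 13.74/1,000 = 98.10. Power = Φ(√(d/4) × ln(1.8/0.84) − 1.960) = Φ(4.952 × 0.7621 − 1.960) = Φ(1.814) = 0.965. With fewer matched patients at the same risk:

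| Pairs lost | Events | Power |
|---|---|---|
| 10% | 88.3 | 0.947 |
| 20% | 78.5 | 0.922 |
| 30% | 68.7 | 0.885 |
| 50% | 49.1 | 0.761 |

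**5. Could the hazard ratio be shifted?** Only an illustration on assumed inputs is possible. Let 30% of matched apixaban patients and 50% of matched warfarin patients enter in an early era with relative outcome risk R. The bias factor is (1 + 0.3(R − 1)) / (1 + 0.5(R − 1)).

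- R = 2.0: 1.30/1.50 = 0.867, so a true 0.84 appears as 0.73.
- R = 1.25: 1.075/1.125 = 0.956, giving 0.80.
- R = 0.5: 0.85/0.75 = 1.133, giving 0.95.
- Equal early shares: factor 1, no bias.

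The documents supply neither the shares nor R, so neither the direction nor the size is known.

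**The case against.** The strongest reply is that the analysis is matched, and after matching the suggestive rows balance. If they proxy era, era may be largely balanced; if they do not, they are no evidence of imbalance. Other matched figures do not show late apixaban entry either. Censoring at the specified date is 11.88% on warfarin and 12.13% on apixaban. Prior database history is slightly longer on warfarin in all three databases (1,631 vs 1,568, 2,204 vs 2,093 and 720 vs 682 days), which is not what earlier warfarin entry would tend to produce if data start dates are fixed.

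This rules out calling era an uncontrolled confounder. It does not close the point. Balance on proxies is incidental, cannot be checked without an index-date row, and says little about trends within the ICD-10 years. Date censoring covers only about 12% of patients.

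The proxy reading is itself an inference. Malignant hypertension is the weakest of the three rows: Optum, with the longest window, shows only 0.6% vs 0.1%. Appendix A also excludes patients with the ICD-9 malignant hypertension code, so the covariate must use a definition that is not shown.

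A reader might also note that apixaban's share of the unmatched cohort rises with the end of data: 40.6% in Medicare, 61.1% in MarketScan and 65.4% in Optum. That does not support the point. The databases differ in payer and age as well as end date, and matching gives equal arms within each.

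Finally, one database already has a pre-match c-statistic of 0.938, and Optum matched only 490 of 1,472 warfarin patients, so another treatment predictor could cost pairs. That objection stands and is priced above.

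**Conclusion.** The omission is a matter of record: entry date is not directly controlled, examined or reported. That it matters is plausible but unproven. The unmatched tables suggest an era difference between arms within databases. That rests on reading CHA2DS2-VASc, sleep disorder and malignant hypertension as coding-sensitive, and the covariate code lists are not shown.

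It would be tempting to conclude that era confounds the matched comparison across 2014–2020. The documents do not support that. Only Optum reaches 2020, and it supplies 980 of 7,140 matched patients (13.7%). The proxies balance after matching. No index-date distribution by arm and no outcome rate by year is given, so no era–outcome association is shown and the effect on the hazard ratio cannot be sized. The stated power figures are correct on their inputs and are not in dispute.

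Confidence is moderate. The change should be made because it is cheap and would turn an unverifiable assumption into a checked one.

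**What to change.** Before any outcome comparison, add calendar period of the index date (for example half-year or year) to each database-specific propensity score, or match within calendar period. Add it as a row in Table 1, with its distribution and standardised difference by arm before and after matching.

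The variable is already in the data. The cost is one rerun of the matching and some lost pairs, most likely in Optum with its 490 pairs. Losing every Optum pair would remove 13.7% of matched patients, which lies between the 10% and 20% rows of the power table. If losses prove larger, the minimum is to report index year by arm before and after matching, and to name in section 13.2 a sensitivity analysis restricted to ICD-10-era entry.

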#### 5.2.2 Specify inclusion/exclusion criteria for cohort entry and define the index date.

Inclusion and exclusion criteria were adapted from the trial as closely as possible. Definitions for all inclusion/exclusion are provided in **Appendix A** and are summarized in the flowcharts below.

### 5.3 Flowchart of the study cohort assembly

|                                    | Optum                  |                    | Marketscan             |                    | Medicare               |                    |
|------------------------------------|------------------------|--------------------|------------------------|--------------------|------------------------|--------------------|
|                                    | Less Excluded Patients | Remaining Patients | Less Excluded Patients | Remaining Patients | Less Excluded Patients | Remaining Patients |
| All patients                       |                        | 77,673,639         |                        | 200,203,908        |                        | 6,886,908          |
| Did not meet cohort entry criteria | -76,868,532            | 805,107            | -
199,645,422       | 558,486            | -4,150,733             | 2,736,175          |

Effectiveness research with Real World Data to support FDA's regulatory decision making

|                                                                                                                                                                                                                                                                                                                                               |          |         |          |         |            |           |
|-----------------------------------------------------------------------------------------------------------------------------------------------------------------------------------------------------------------------------------------------------------------------------------------------------------------------------------------------|----------|---------|----------|---------|------------|-----------|
| Excluded due to insufficient enrollment                                                                                                                                                                                                                                                                                                       | -101,912 | 703,195 | -39,077  | 519,409 | -53,978    | 2,682,197 |
| Excluded due to prior use of referent                                                                                                                                                                                                                                                                                                         | -347,539 | 355,656 | -307,198 | 212,211 | -1,789,291 | 892,906   |
| Excluded due to prior use of exposure and because patient qualified in >1 exposure category                                                                                                                                                                                                                                                   | -254,675 | 100,981 | -137,453 | 74,763  | -554,606   | 338,300   |
| Excluded based on Age                                                                                                                                                                                                                                                                                                                         | 0        | 100,981 | 0        | 74,758  | -104       | 338,196   |
| Excluded based on Gender                                                                                                                                                                                                                                                                                                                      | 0        | 100,981 | 0        | 74,758  | 0          | 338,196   |
| Excluded based on Use of other NOACs (rivaroxaban, dabigatran, edoxaban)                                                                                                                                                                                                                                                                      | -5,094   | 95,887  | -3118    | 71,640  | -19004     | 319,192   |
| Excluded based on Inclusion # 3a - Acute Symptomatic Proximal DVT                                                                                                                                                                                                                                                                             | -82,653  | 13,234  | -60406   | 11,234  | -277,170   | 42,022    |
| Excluded based on Inclusion # 3b - Acute Symptomatic PE and based on Inclusion # 4 - Age                                                                                                                                                                                                                                                      | -4,641   | 8,593   | -2852    | 8,382   | -21,229    | 20,793    |
| Excluded based on Exclusion # 1 - pregnancy                                                                                                                                                                                                                                                                                                   | -14      | 8,579   | -42      | 8,340   | -22        | 20,771    |
| Excluded based on Exclusion # 6 - Thrombectomy, Insertion of Caval Filter, or Use of Fibrinolytic Agent                                                                                                                                                                                                                                       | -211     | 8,368   | -143     | 8,197   | -24        | 20,747    |
| Excluded based on Exclusion # 7 - Active bleeding (HAS_BLED Score >=3), based on Exclusion # 10A - Mechanical Valve, and based on Exclusion # 11.1 - Intracranial Bleeding                                                                                                                                                                    | -3,708   | 4,660   | -1447    | 6,750   | -11,558    | 9,189     |
| Excluded based on Exclusion # 11.2 - Intraocular Bleeding                                                                                                                                                                                                                                                                                     | 0        | 4,660   | 0        | 6,750   | 0          | 9,189     |
| Excluded based on Exclusion # 11.3 - Gastrointestinal Bleeding                                                                                                                                                                                                                                                                                | -12      | 4,648   | -52      | 6,698   | -78        | 9,111     |
| Excluded based on Exclusion # 11.4 - Head Trauma or Other Major Trauma                                                                                                                                                                                                                                                                        | -60      | 4,588   | -65      | 6,633   | -96        | 9,015     |
| Excluded based on Exclusion # 11.5 - Major Surgery, Exclusion # 11.6 - Ischemic Stroke, Exclusion # 11.7 – Neurosurgery, Exclusion # 11.8 - Gross Hematuria, Exclusion # 11.9 - Non - healing surgical wound, Exclusion # 11.10 - Intracranial neoplasm, arteriovenous malformation or aneurysm, and Exclusion # 11.11 - Overt Major Bleeding | -57      | 4,531   | -33      | 6,600   | -111       | 8,904     |
| Excluded based on Exclusion # 11.12 - Coagulation defects or malignant neoplasm of tissue                                                                                                                                                                                                                                                     | -36      | 4,495   | -20      | 6,580   | -33        | 8,871     |
| Excluded based on Exclusion # 12 - active liver disease                                                                                                                                                                                                                                                                                       | -133     | 4,362   | -142     | 6,438   | -226       | 8,645     |
| Excluded based on Exclusion # 13 - CCI >= 10 and based on Exclusion # 14 - Bacterial Endocarditis                                                                                                                                                                                                                                             | -39      | 4,323   | -33      | 6,405   | -28        | 8,617     |

|                                                                                                                             |     |              |     |              |      |              |
|-----------------------------------------------------------------------------------------------------------------------------|-----|--------------|-----|--------------|------|--------------|
| Excluded based on Exclusion # 15 - Uncontrolled Hypertension and based on Exclusion # 16 - thrombocytopenia                 | -26 | 4,297        | -36 | 6,369        | -78  | 8,539        |
| Excluded based on Exclusion # 17 – anemia, Exclusion # 18 - CKD/ESRD, and Exclusion # 22 - Heparin-induced thrombocytopenia | -33 | 4,264        | -31 | 6,338        | -139 | 8,400        |
| Excluded based on Exclusion # 27 - aspirin (ASA) >165 mg                                                                    | 0   | 4,264        | 0   | 6,338        | 0    | 8,400        |
| Excluded based on Exclusion # 28 - ASA plus clopidogrel or ASA plus ticlopidine                                             | 0   | 4,264        | 0   | 6,338        | 0    | 8,400        |
| Final cohort                                                                                                         |     | 4,264 |     | 6,338 |      | 8,400 |

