# Appendix A

| AMPLIFY trial definitions                                                                                                                                                                                                                                                                                                                                                                                                                                                                            | Implementation in routine care                                                                                                                                                                                                                              | Please see the following Google Drive for further details or any missing information:
https://drive.google.com/drive/folders/1WD618wrvwYIeaXzflTcuK-VCcnb6b-gV?usp=sharing |                                                                                                                                                                                                                                                                                                                                                                                                                                                                                                                    |

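### Section 5.1 admits DVT, PE or both, but the flowchart applies the two criteria one after the other and leaves almost no patients with DVT alone

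*Combined protocol and SAP*

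**What the plan says.** Section 5.1 describes this study, not the randomised trial, and says: "We will restrict the analyses to patients with a diagnosis of proximal DVT, PE, or both". The target has the same shape. Section 1.2 gives the trial's aim as a comparison "in patients with symptomatic deep vein thrombosis (DVT), pulmonary embolism (PE), or both". In Appendix A, the column headed "AMPLIFY trial definitions" lists DVT and PE as alternatives, either of which qualifies. Section 1 calls the trial one "that the described real-world evidence study is trying to replicate as closely as possible", and Section 5.2.2 adds: "Inclusion and exclusion criteria were adapted from the trial as closely as possible".

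The flowchart in Section 5.3 has two successive rows. The first is "Excluded based on Inclusion # 3a - Acute Symptomatic Proximal DVT". The next is "Excluded based on Inclusion # 3b - Acute Symptomatic PE and based on Inclusion # 4 - Age". An age row, "Excluded based on Age", already stands higher up.

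In the implementation column of Appendix A, the ICD-10 list for the DVT criterion includes I26.xx, printed twice, alongside I80.xx to I82.xx. I26.xx is also the ICD-10 code for the PE criterion. The ICD-9 list for DVT (451.xx, 453.xx) contains no PE code.

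**The concern.** A rule that admits DVT, PE or both is one criterion. Someone who qualifies through DVT cannot then fail for lacking PE. Two successive exclusion rows, each removing many patients, amount to a PE requirement, and a PE requirement drops patients whose only qualifying event is DVT.

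At stake is what the replication can be compared with. The benchmark of 0.84 (Section 1.6) and the margin of 1.8 (Section 1.4) come from a trial of DVT, PE or both. Setting an almost entirely PE cohort against them, while describing it as the Section 5.1 population, leaves agreement or disagreement unreadable for patients with DVT and no PE. An analysis within the built cohort cannot recover patients who were removed before it was formed.

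**Working it through.** **1. Flowchart rows (Section 5.3).** The subtractions reproduce in all three databases.

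| | Left after 3a | Removed at 3b/age | Left after 3b/age | Share removed |
|---|---|---|---|---|
| Optum | 13,234 | 4,641 | 8,593 | 35.1% |
| MarketScan | 11,234 | 2,852 | 8,382 | 25.4% |
| Medicare | 42,022 | 21,229 | 20,793 | 50.5% |
| Total | 66,490 | 28,722 | 37,768 | 43.2% |

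Under an either/or rule the expected number removed at 3b, age aside, is 0.

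**2. How much of the row could be age?** The criterion is 18 years or older (Appendix A). The earlier age row lists 0, 0 and 104 removals; for Medicare that is 104/338,300 = 0.03%. Medicare also supplies 21,229/28,722 = 73.9% of the 3b/age row. A large age component is therefore implausible, but the exact split is not given, so 28,722 stays an upper bound for the PE step.

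**3. PE and DVT flags in the unmatched table (Appendix B).**

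- PE: Optum 1,472 + 2,783 = 4,255 of 4,255; MarketScan 2,457 + 3,874 = 6,331 of 6,338; Medicare 4,964 + 3,400 = 8,364 of 8,389. Total 18,950 of 18,982 (99.8%), so 32 lack the flag (0, 7 and 25).
- DVT: 861 + 1,392 + 1,610 + 1,981 + 2,794 + 1,519 = 10,157 of 18,982 (53.5%).

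The flowchart ends at 4,264 + 6,338 + 8,400 = 19,002, which is 20 more than the table, so the shares use 18,982.

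**4. The same flags after matching.**

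- PE: 3,563 + 3,566 = 7,129 of 7,140, so 11 lack the flag (0.15%).
- DVT: 1,838 + 1,836 = 3,674 of 7,140 (51.5%).

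Anyone with DVT and no PE must lack the PE flag. By these flags there are at most 32 such patients before matching and 11 after. PE is near-universal in every arm of every database and DVT is present in about half, which is the pattern of PE required and DVT optional.

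**5. Likely mechanism (inferred).** Because I26.xx sits in the printed DVT list, a PE patient coded in ICD-10 passes 3a without any DVT. Step 3b then keeps only PE. That would produce the cohort seen.

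**6. Power (Section 10).** With D events and 1:1 allocation, power = Φ(ln(1.8/HR) × √(D/4) − 1.96). With D = 7,140 × 13.74/1,000 = 98.1036:

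- HR 0.84: 0.965, matching the plan's pooled figure of 0.965194245.
- HR 1.00: 0.83.
- HR 1.18 (upper limit of the trial's overall interval): 0.55.

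The last two values only illustrate how far the power rests on carrying 0.84 over to a PE cohort. They are not estimates for PE patients; the documents give none.

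**The case against.** The strongest reply accepts the disagreement and contests its certainty and size.

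- **A reason may exist elsewhere.** Appendix A points to an external folder for further details and missing information, and the design diagram is not readable here. This stands as a limit: the claim is that no reason appears in the text available.
- **The age argument is weak.** Ages in Appendix B describe patients who had already passed the age criterion, so they cannot show how many failed it, and the earlier age row is not defined. This is fair. The Appendix B flags carry the case, and the age row only makes a large age share implausible.
- **43% overstates the loss.** It is counted before all later exclusions, and the printed DVT ranges are broad, so many of those removed may never have had acute proximal DVT. This also stands. The eligible loss is unknown, and no gain in cohort size is projected.
- **The flags are undefined.** If the PE flag covered more than PE, Appendix B would say less. Even then, the 3b row would remain unexplained under Section 5.1.
- **The cohort is a valid subset.** Patients with PE do meet the Section 5.1 rule, and this point does not by itself bias the comparison between the drugs. That is true, but the study exists to be set against a trial estimate, so who is in the cohort determines what that comparison means.
- **Dropping I26.xx from the DVT list is cosmetic.** Under an either/or rule the union of codes is unchanged. Agreed; it only makes the two lists match their labels, and done without the either/or rule it would exclude patients with PE alone.

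**Conclusion.** The concern holds. Section 5.1 and the built cohort disagree, and nothing in the readable text states or justifies the difference. The 3b/age row removes 28,722 of 66,490 patients (43%), an upper bound for the PE step, where an either/or rule would remove none for lacking PE. By the Appendix B flags, at most 32 of 18,982 unmatched patients (0.17%) and 11 of 7,140 matched patients (0.15%) can have DVT without PE.

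Confidence is high that text and cohort disagree. It is lower on the mechanism, which is inferred from the printed codes; the full code lists are held elsewhere. The patient counts also assume that the undefined PE flag means what its label says. Pooled power is not the complaint. The problem is who is studied and what a comparison with 0.84 and 1.8 can support. It must be resolved before the comparative analysis.

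**What to change.** Choose one of two routes before Section 13, which is still blank.

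**Route A: build the cohort that Section 5.1 describes.** Code inclusion 3 as a single criterion, a qualifying DVT or a qualifying PE, with the same logic in ICD-9 and ICD-10, and show it as one flowchart row separate from age. Take I26.xx out of the DVT list. Check that list against the plan's own acute and proximal wording: labels printed in the Appendix A outcome list show that the 453.xx range includes distal and chronic codes, and under an either/or rule this list alone would admit patients without PE. Define the DVT and PE flags in Appendix B. Re-run Sections 5.3 and 7 to 10, repeat the reviews, and report DVT without PE separately.

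*Cost:* a re-run of the cohort build, feasibility, matching, balance and power, plus renewed review by the principal investigators, FDA and advisory board. No new data are needed, and it can be done before any treatment effect is seen.

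**Route B: keep a PE-required cohort on purpose.** State and justify it in Section 5.1 and in the implementation column of Appendix A; Section 1.2 describes the trial and should stay as it is. Limit the conclusions to patients with PE. State explicitly that the 0.84 and 1.8 from the whole trial population are assumed to apply to them, and have the power inputs reviewed again.

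*Cost:* lower, but more than a text edit, because the benchmark assumption and the power inputs need fresh review.
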